4.5 Restrictions during the study

There are no certain restrictions during the study.

4.6 Withdrawal of subjects and study stop

Subjects are free to discontinue their participation in the study at any time without prejudice to further treatment. The subjects may be withdrawn from the study at the discretion of the investigator due to safety concerns or if judged non-compliant with study procedures. Other reasons for discontinuing a subject are incorrect enrolment and subjects lost to follow-up.

A subject who discontinues will be asked about the reason(s) for discontinuation and the presence of any adverse events. If possible, they will be seen and assessed by the investigator. Adverse events will be followed up.

Also, the manufacturers of the study drugs may revoke their products, which may lead to the entire study may be interrupted.

4.6.1 Premature termination of the study

The Sponsor/Investigator may decide to stop the trial or part of the trial at any time. If a trial is prematurely terminated or suspended, the Investigator should promptly inform the patients and ensure appropriate therapy and follow-up. Furthermore, the Investigator should promptly inform the Ethics committee and provide a detailed written explanation. The regulatory authority should be informed according to national regulations.

5. TREATMENTS

Puregon®, Nebido® and Testoviron Depot® will be administrated in the study.

Table 3 *Identity of investigational product(s)*

Investigational product	Dosage form and strength	Administration dose	Manufacturer
Puregon®- Follitropin beta	Solution for injection s.c. 300 IE/0.36 mL	30-75 IE, 3 times a week	MSD
Nebido®	Solution for injection i.m. 1000 mg/4mL	200mg (at start and after 3 months) in group I and 250 mg in group II	Bayer
Testoviron Depot®	Solution for injection i.m. 250mg/mL	0.2mL=50 mg per month in group I 0,3ml=75mg per month in group II (total 6 injections)	Bayer Shering Pharma AG

Puregon (rhFSH) and Nebido are indicated in men with hypogonadotrop, hypogonadism and testosterone deficiency. Testoviron Depot is the most common testosterone ester for substitution therapy when testosterone deficiency has been confirmed.

Other common side effects are skin reactions at the application site, headache, gastro-intestinal, insomnia.

Testoviron Depot gives a pronounced variation in testosterone levels in the blood, with the highest values the day after injection and then gradually decreasing levels until the next scheduled injection.

Nebido provide a more steady level of testosterone in the blood between dosing sessions.

Testoviron Depot is currently not registered in Sweden and will be prescribed on license.

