3. STUDY DESIGN AND PROCEDURES

3.1 Overall study design and flow chart

This is a prospective, randomized, controlled, open clinical study with parallel-group design. A total of 70 young males with delayed or absent puberty will be randomized to receive hormone replacement during 6 or 12 months. The study includes 9 or 10 visits at the clinic during a total period of 12 months.

To not expose boys for a new treatment (Nebido and Puregon in group I and Nebido in group II) that is inferior to Stand of Care Testoviron, a fertility test will be performed after 10 evaluable patients in each arm in the groups.

The subjects will be divided to two groups depending on whether they have I) absences of puberty (n=30) or II) delayed/slow progress of puberty (n=40):

I) Boys with absence of puberty (testis 1-3 mL and morning testosterone less than 0.5nM) will be randomized to two alternative pubertal replacement therapies; 1) low dose of Testoviron Depot® (SoC) 50 mg i.m. injection once a month or 2) rhFSH (Puregon®) and low dose Nebido® (one injection of 200 mg every 3 months). Those randomized to receiving rhFSH (Puregon®) and low dose Nebido® will start both treatments concomitant. The rhFSH (Puregon®) dose will be adjusted to reach serum FSH levels of 3-5IU/ml (see appendix D). This is expected to happen within one month (first check after one week after start of treatment with Puregon) and if not reach within one month of start of Puregon treatment the patient will be withdrawn from the study. Boys who have been randomized to Puregon/Nebido but at inclusion have serum levels of FSH above 3 will not be treated with Puregon, but if the patient during the study on 2 concomitant visits have serum FSH below 3IU/L he will be treated with Puregon to achieve serum FSH levels 3-5 IU/L during the rest of the study (see appendix D). The treatment will continue for 12 months. The effect will be evaluated after 6 and 12 months respectively on the development of masculinization and on spontaneous start of puberty. If the spontaneous puberty has started, the pubertal hormone replacement treatment will be stopped. The Nebido treatment will be dose adjusted in patients after the 1st injection if the testosterone profile shows to high or low levels; the goal is to have similar levels during 2 months as in early puberty (1-3 nM). For individual Nebido® adjustments in group I see appendix D.

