II) Boys with delayed/slow progress of puberty (testis 4-6 mL and morning testosterone less than 4 nM) will be randomized to receive either 1) Testoviron Depot® (SoC) 75 mg i.m. injection once a month (SoC) or 2) Nebido® one injection of 250 mg at start and after 3 month. The treatment will continue for 6 months, dose adjustments will be possible after the first 4 patients on Nebido® (250 mg) for the rest of the study. The aim for the Nebido® treatment is to have morning testosterone levels in the lower range of mid puberty (4-9 nmol/L). An interim analysis has to be done after the first 5 patients and thereafter keep or adjust the dose (see appendix D for adjustment of the Nebido® dose for group II). The treatment will be evaluated after 6 month on development of masculinization and on spontaneous start of puberty after 12 months.

Figure 1 and Table 1 show the study overview and activities.

Figure 1a Study design Group I (absence of puberty)

[figure not shown]

Figure 1b Study design Group II (delayed puberty)

[figure not shown]

Table 1 Study activities

	Visit 1	Visit 2	Visit 3	Visit 4	Visit 5	Visit 6	Visit 7	Visit 8	Visit 9*	Visit 10
	Pre-	0	2 days	7 days	1 month	2 months	3 months	6 months	9* months	12 months
Informed consent	X									
Demography	X									
Medical history	X									
Nicotine use	X									
Weight, height	X						X	X	X	X
Pulse, blood pressure	X									
Physical exam	X									
Bone-age	X									
LHRH test	X									X*
Pubertal stage	X						X	X	X	X
HQOL	X							X		X
Hb, liver enzymes	X						X	X		X
LH, FSH	X	X		X*	X		X	X	X	X
DHEAS,		X						X		X
Incl/excl criteria		X								
Study drug		X								
Testosterone, estradiol		X	X	X	X	X	X	X		X

SHBG, AMH, InhibinB		X			X			X		X
Signs of masculinization								X		X
Plasma for masspektometri of steroids	X							X		X
Adverse events	X	X	X	X	X	X	X	X	X	X
Serious Adverse event recording	X	---	---	---	---	---	---	---	---	---

*Visit 9: Group I only

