5.1.1 Doses and treatment regimens

Lowest possible starting doses will be administrated.

Puregon® solution (rhFSH) for injection subcutaneously in ampoules of 300 IE/0.36 mL, will be administrated as multiple doses (3 times per week) to boys randomized to Puregon/Nebio who have serum FSH levels below 3 IU/L Group I. The first dose of Puregon will be given at the clinic under medical supervision to rule out any hypersensitivity reactions immediately after dosing. Otherwise it will be used and handled according to manufacturer instruction. Boys who at inclusion have serum levels of FSH above 3, but during the study on 2 concomitant visits have serum FSH below 3 IU/L will be offered to start Puregon treatment to achive serum FSH levels reached 3-6 IU/L during the rest of the study.

Nebido® a solution for injection 1000 mg/4mL and 200 mg or 250 mg will be administrated every 3rd month s. For patients on Nebido® in group I, an evaluation of the testosterone profile will be done

after the first injection and possibility to adjust the dose. For patients in group II an interim analysis on testosterone levels will be done after 4 patients in each group for the possibility to titrate up or down for the remaining study period. For Puregon® (rhFSH) dosing see appendix D

Group I: Individual dosing on the basis that the testosterone level should be between 2-4 nM during 8 of 12 weeks. The dose may be adjusted up or down with intervals of 50 mg.

Group II: A dose check will be made after the first 4 boys. If the testosterone levels are between 4-9 nM during 8 of 12 weeks, the dose may be adjusted up or down with intervals of 50 mg. See appendix D

The aim for Nebido® treatment is to have morning testosterone levels in the mid or upper early puberty range (1-3 nM) for boys with absence of puberty (group I) and the lower range of mid puberty (4-9 nmol/L) for boys with delayed puberty (Group II). See appendix D

Testoviron Depot® is given once a month intra muscular and the dose will be 50 mg in group I and 75 mg in group II (SoC; no dose adjustment).

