5.3 Treatment compliance

No uncertainty about compliance will exist when injections (Nebido and Testoviron) are administered under the supervision of the study nurse at the clinic.

The unbroken ampoules (Testoviron) will be assessed against the dispensed amount. Subjects will be asked to collect empty patch envelopes and ampoules and bring to study visits. Any discrepancies should be discussed with the patient and commented upon in the CRFs.

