6.3 LHRH-test

The LHRH-test will be performed in the Group I subjects at visits 1, 8 and 10.

At visit 8 (after 6 months) the LHRH-test will be performed in the morning, before the first Nebido injection is given. In the Testoviron- arm, the LHRH-test will be made same day as Testoviron administration but prior to the injection itself.

At visit 10 (after 12 months) the LHRH-test will be performed same day as the Nebido/Testoviron injections but prior to the injection itself.

The LHRH-test involves injecting synthetic LHRH into a vein and measuring blood for LH and FSH levels (which, if the pituitary is functioning normally, will rise). A blood sample is taken before the injection, then 20 and 60 minutes afterwards. A cannula is placed in a vein in the arm to enable the nurse to give the LHRH and take samples. Side-effects are rare, but can include nausea, headache and flushing.

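### The SAP gives two Group I Nebido schedules, 2 or 4 scheduled injections before the month-12 primary LH test, and section 6.3 does not settle which applies

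*SAP*

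**What the plan says.** For the Puregon/Nebido arm of Group I, SAP 3.1 specifies rhFSH plus "low dose Nebido® (one injection of 200 mg every 3 months") and adds, for the group: "The treatment will continue for 12 months". SAP 5.1.1 gives the same interval for both groups, "200 mg or 250 mg will be administrated every 3rd month", but no duration.

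SAP section 5, Table 3, states the Nebido dose as "200mg (at start and after 3 months) in group I and 250 mg in group II". The timing bracket is attached to Group I, and Group II has no timing in that cell. In SAP 3.1 almost the same timing belongs to Group II: "Nebido® one injection of 250 mg at start and after 3 month", within a 6-month treatment.

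SAP 6.3 schedules the Group I LHRH test at visits 1, 8 and 10. It places the month-6 test ahead of the first Nebido injection. For month 12 it says that "the LHRH-test will be performed same day as the Nebido/Testoviron injections but prior to the injection itself". SAP section 8 makes the pubertal LH response at 12 months the Group I primary endpoint. Table 1 marks study drug at visit 2 only.

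**The concern.** The Group I primary endpoint is one LHRH test at month 12, compared between the Testoviron arm and the Puregon/Nebido arm. What that comparison means depends on how much testosterone the Nebido boys have had and how recently. The plan itself treats the timing of the test against the injection as important, because 6.3 requires the test before that day's injection.

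Under one passage the Nebido boys are tested at the end of a 3-month dosing interval. Under another they are tested 9 months after their last injection. The comparator is given monthly. These are two different comparisons under one endpoint name. Table 3 is the investigational-product table, so a site could reasonably work from it.

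**Working it through.** **Inputs.** Table 3: Group I 200 mg at months 0 and 3. SAP 3.1: Group I 200 mg every 3 months, duration 12 months; Group II treated for 6 months. SAP 6.3: the month-12 test precedes any injection that day. Appendix D: after the visit 6 (month 2) testosterone value, the Group I dose may change to 150 mg or 250 mg, so month 3 is the first dose affected.

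**Counting rule.** Count injections at 0, d, 2d, … strictly before the end of a period D. When d divides D, n = D/d.

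**Check against the plan's own figures.** Monthly Testoviron over 6 months: 6/1 = 6, which agrees with "0,3ml=75mg per month in group II (total 6 injections"). Nebido every 3 months over 6 months: 6/3 = 2, which agrees with the Group II text in 3.1. The rule reproduces both.

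**Group I Nebido before the month-12 test.** Under 3.1: 12/3 = 4 injections, at months 0, 3, 6 and 9. Under Table 3: 2 injections, at months 0 and 3. With dose a from month 3 onward, the total is 200 + (n − 1) × a.

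| Dose from month 3 | 3.1 (n = 4) | Table 3 (n = 2) | Ratio |
|---|---|---|---|
| 200 mg (nominal) | 200 + 3×200 = 800 mg | 200 + 200 = 400 mg | 2.00 |
| 250 mg | 200 + 3×250 = 950 mg | 200 + 250 = 450 mg | 2.11 |
| 150 mg | 200 + 3×150 = 650 mg | 200 + 150 = 350 mg | 1.86 |

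**Early stop.** SAP 3.1 ends replacement once spontaneous puberty has started. If a boy stops at month 6 before that injection, the ratio is 400/400 = 1.0. If month 6 is his last injection, it is 600/400 = 1.5.

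**Time from last injection to test.** Under 3.1: 12 − 9 = 3 months. Under Table 3: 12 − 3 = 9 months.

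**Section 6.3 against each schedule.**

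| Statement in 6.3 | Table 3 (months 0, 3) | 3.1 (months 0, 3, 6, 9) |
|---|---|---|
| Month-6 test comes before the first Nebido injection | Does not fit: two already given | Does not fit: two already given |
| A Nebido injection is due on the day of the month-12 test | Does not fit: dosing ended at month 3 | Compatible only if dosing goes on at month 12 |

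So 6.3 cannot be used to choose between the two.

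**The case against.** The strongest reply is that the bracket in Table 3 has simply been placed beside the wrong group. SAP 3.1 uses nearly the same timing for Group II, and 6.1.2 and 6.5 speak of 12 months of treatment. That is plausible, but the document does not say so, and the passages still disagree. Figures 1a and 1b are not shown and may carry an injection calendar. If they do, Table 3 would still need to be brought into line with it.

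Several stronger readings are tempting and are not supported:

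- **That exposure differs by at least two-fold.** Two is the ratio at the nominal dose, not a lower bound: down-titration gives 1.86 and early stopping less.
- **That five injections (1000 mg) precede the test.** Any month-12 injection follows the test, and 5.2 and 6.1.2 leave room for it to be post-study care.
- **That 5.1.1 states a 12-month course.** It gives only the interval; the duration comes from 3.1.
- **That the Testoviron total of 6 is an error.** It directly follows the Group II dose and matches a 6-month monthly course.
- **That boys within the trial will be on different schedules.** No passage provides for both to run side by side. The ambiguity concerns which one is meant.
- **That Testoviron doses are unsupervised or missed.** Months 4, 5, 7, 8, 10 and 11 have no numbered visit, and 5.3 says "Subjects will be asked to collect empty patch envelopes and ampoules and bring to study visits" beside a statement about injections supervised in clinic. But Table 1 does not confine injections to numbered visits, and supervision and ampoule counts can complement each other. This is at most a supporting note.

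**Conclusion.** The contradiction stands. Table 3 and 3.1 give different Group I Nebido schedules: 2 injections (400 mg) against 4 (800 mg) at the nominal dose before the primary test, a ratio of 2.0. With Appendix D titration from month 3 the ratio is about 1.9 to 2.1, and it falls to between 1.0 and 1.5 for a boy who stops at month 6. The last injection is 9 or 3 months before the test.

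These figures assume that month 0 counts, that a month-12 injection does not count as exposure before the test, and that the boy is otherwise dosed as scheduled. The point is more than clerical because it leaves open the treatment that the Group I primary comparison evaluates. It does not show that any boy was or will be wrongly dosed, and it does not show which schedule is the intended one.

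**What to change.** Reconcile Table 3 and SAP 3.1, 5.1.1 and 6.3 to one stated Group I Nebido injection calendar. The sponsor states which schedule is intended; this review takes no position on that. Specifically:

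- give the planned injection months and the injection count for each group;
- correct the month-6 wording in 6.3 so that it fits the calendar, and say whether a month-12 injection is study treatment or later care;
- align the study-drug row of Table 1 with the calendar.

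While the text is open, it would help to make clear in 5.3 who supervises injections that fall between numbered visits, and to have the CRF carry the date of each injection. SAP 5.2 already requires every administration of study drug to be recorded, so only the explicit date would be new.

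The cost is protocol and CRF wording. No extra patients are needed.

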5.1.1 Doses and treatment regimens

Lowest possible starting doses will be administrated.

Puregon® solution (rhFSH) for injection subcutaneously in ampoules of 300 IE/0.36 mL, will be administrated as multiple doses (3 times per week) to boys randomized to Puregon/Nebio who have serum FSH levels below 3 IU/L Group I. The first dose of Puregon will be given at the clinic under medical supervision to rule out any hypersensitivity reactions immediately after dosing. Otherwise it will be used and handled according to manufacturer instruction. Boys who at inclusion have serum levels of FSH above 3, but during the study on 2 concomitant visits have serum FSH below 3 IU/L will be offered to start Puregon treatment to achive serum FSH levels reached 3-6 IU/L during the rest of the study.

Nebido® a solution for injection 1000 mg/4mL and 200 mg or 250 mg will be administrated every 3rd month s. For patients on Nebido® in group I, an evaluation of the testosterone profile will be done

after the first injection and possibility to adjust the dose. For patients in group II an interim analysis on testosterone levels will be done after 4 patients in each group for the possibility to titrate up or down for the remaining study period. For Puregon® (rhFSH) dosing see appendix D

Group I: Individual dosing on the basis that the testosterone level should be between 2-4 nM during 8 of 12 weeks. The dose may be adjusted up or down with intervals of 50 mg.

Group II: A dose check will be made after the first 4 boys. If the testosterone levels are between 4-9 nM during 8 of 12 weeks, the dose may be adjusted up or down with intervals of 50 mg. See appendix D

The aim for Nebido® treatment is to have morning testosterone levels in the mid or upper early puberty range (1-3 nM) for boys with absence of puberty (group I) and the lower range of mid puberty (4-9 nmol/L) for boys with delayed puberty (Group II). See appendix D

Testoviron Depot® is given once a month intra muscular and the dose will be 50 mg in group I and 75 mg in group II (SoC; no dose adjustment).

5.1.2 Labelling

The label will include the following information:

Study code, randomisation code, name of investigational product, pharmaceutical dosage form, strength, quantity, dosage instructions, name of investigator (to be filled in at study site), expiry date, order number, storage instruction, “for clinical study use only”, “Keep out of the reach of children”, name, address and telephone number of sponsor

5.1.3 Storage

All study drugs must be kept in a secure place under appropriate storage conditions. Puregon will be stored at 2 °C- 8 °C. Appropriate storage conditions as specified on the investigational product label will be followed.

5.2 Concomitant medication and post-study treatment(s)

Medication, which is considered necessary for the subject’s safety and well-being, may be given at the discretion of the investigator. The administration of all medication (including investigational product) must be recorded in the appropriate sections of the case report form (CRF).

At the end of the study decision of continued treatment will be made.

5.3 Treatment compliance

No uncertainty about compliance will exist when injections (Nebido and Testoviron) are administered under the supervision of the study nurse at the clinic.

The unbroken ampoules (Testoviron) will be assessed against the dispensed amount. Subjects will be asked to collect empty patch envelopes and ampoules and bring to study visits. Any discrepancies should be discussed with the patient and commented upon in the CRFs.

5.3.1 Accountability

It is the investigator's responsibility to establish a system for handling investigational medicinal products to ensure that it is correctly received and recorded and only dispensed to trial subjects in accordance with this protocol and manufacturer instructions.

6. STUDY MEASUREMENTS AND VARIABLES

6.1 Screening and demography

Each subject will undergo a pre-entry medical examination 5-14 days prior to the first study day. This will consist of:

- Information and signed consent
- Demographic data - date of birth, birth weight and length, current height and weight,
- Habits of nicotine
- Past and present medical including family history
- Present medications
- Pulse, systolic and diastolic blood pressure
- Physical examination including cardiovascular and respiratory systems, abdomen, general appearance, skin, head and neck, lymph nodes, thyroid and reflexes and specification of abnormalities
- Bone age
- Health-related quality of life (KIDSCREEN, JTJÄ)
- Blood sampling (20 ml) for haematology assessments and clinical chemistry (Table 4)
- Puberty stage (testicular volume and pubic hairiness)

6.1.1 Methods of assessments

According to routine standards at the hospital.

6.1.2 Post-study

After the 12 month treatment period the patient will be followed and treated according clinical routine at the site.

6.2 Bone age

To estimate the maturity of the boy's skeletal system, a single X-ray of the left wrist, hand and fingers will be undertaken. The X-ray image will be compared with X-rays images in a standard atlas of bone development of children of the same gender and age. This is a routine investigation and not an extra research investigation. The bone maturation is measured by two models BP and TW. This shows the maturation of the bone and how much the child still has to grow.

6.3 LHRH-test

The LHRH-test will be performed in the Group I subjects at visits 1, 8 and 10.

At visit 8 (after 6 months) the LHRH-test will be performed in the morning, before the first Nebido injection is given. In the Testoviron- arm, the LHRH-test will be made same day as Testoviron administration but prior to the injection itself.

At visit 10 (after 12 months) the LHRH-test will be performed same day as the Nebido/Testoviron injections but prior to the injection itself.

The LHRH-test involves injecting synthetic LHRH into a vein and measuring blood for LH and FSH levels (which, if the pituitary is functioning normally, will rise). A blood sample is taken before the injection, then 20 and 60 minutes afterwards. A cannula is placed in a vein in the arm to enable the nurse to give the LHRH and take samples. Side-effects are rare, but can include nausea, headache and flushing.

